1. INTRODUCTION

This statistical analysis plan (SAP) is for study 73763989HPB2003 (INSIGHT): A Phase 2 randomized, open-label, parallel-group, multicenter study to assess intrahepatic and peripheral changes of immunologic and virologic markers in response to combination regimens containing JNJ-73763989 (JNJ-3989) and nucleos(t)ide analog (NA) with or without JNJ-56136379 (JNJ-6379) in patients with chronic hepatitis B virus (HBV) infection. Participants who provide separate consent may additionally receive optional treatment with pegylated interferon alpha-2a (PegIFN- α 2a).

This SAP, which is to be interpreted in conjunction with the Clinical Protocol Amendment 6 (finalized on 25 November 2021) and country-specific Amendment 6/FRA-3 (finalized on 25 November 2021), describes the definitions of analysis sets, derived variables, and statistical methods to assess efficacy, safety, and pharmacokinetics/pharmacodynamics (PK/PD) of the study intervention arms. Details of the plasma PK/PD analyses will be described in a separate analysis and modeling plan.

INSIGHT will enroll patients in three study panels. Panel 1 will consist of participants who are HBeAg positive and not currently treated. Panel 2 will consist of participants who are HBeAg negative and virologically suppressed by entecavir (ETV), tenofovir disoproxil (TD), or tenofovir alafenamide (TAF) treatment. Panel 3 will consist of participants who are HBeAg positive or negative and are either not currently treated or virologically suppressed by ETV or TD treatment. Panels 1 and 2 will have one set of objectives and endpoints, while Panel 3 will have its own set. **Note:** The Panel 3 data analysis is for the country-specific Amendment 6/FRA-3 and concerns only 4 patients from France.

As of Protocol Amendment 5, participants who were previously randomized to receive JNJ-6379 treatment had to immediately stop JNJ-6379 and will thereafter receive JNJ-3989 and NA only. New participants will enroll without randomization to receive JNJ-3989 and NA.

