3. SAMPLE SIZE DETERMINATION

This study aims to enroll 18 to 24 participants in total across Panels 1 and 2, i.e., 8 to 12 participants per study panel. In Panel 3, approximately 4-6 participants will be enrolled.

Regarding Panels 1 and 2, due to the exploratory nature of the study, the sample size was determined based on clinical and feasibility considerations related to the liver biopsy procedures performed multiple times during the study, rather than a formal statistical calculation. Nevertheless, a sample size of 8 to 12 participants each in Panel 1 and 2 is considered sufficient to provide adequate precision of the estimate of the primary endpoint (change from baseline to Week 40 in the proportion of HBsAg+ hepatocytes) as estimated by the 80% confidence interval (CI).

For the estimation of the absolute change in the proportion of HBsAg+ hepatocytes from baseline to Week 40 for the overall study population (Panels 1 and 2 combined), the following assumptions were made. Assuming an absolute reduction of 70% in Panel 1 (75% at baseline versus 5% at Week 40) and 29% in Panel 2 (30% at baseline versus 1% at Week 40), and assuming an inter-subject variability of the change equal to 0.5 on the logit scale in both panels, a binomial model ([Kassahun et al 2012](#)) including visit as covariate with normal random effects provides an expected width of the 80% CI of 16.7% for N=24, a width of 17.9% for N=20, and a width of 20.3% for N=16. The point estimates (two-sided 80% CI) are 50.8% (42.5%; 59.1%) with N=24, 50.7% (41.8%; 59.7%) with N=20, and 50.6% (40.5%; 60.8%) with N=16.

For the between-panel difference in the absolute reduction in the proportion of HBsAg+ hepatocytes from baseline to Week 40 using the binomial model described above augmented with panel as an additional covariate and the same inter-subject variability, the estimated width of the two-sided 80% CI around the difference (Panel 1 – Panel 2) is 17.6% for N=24 (12 per panel), 19.3% for N=20 (10 per panel), and 21.2% for N=16 (8 per panel). The point estimates (80% CI) are 40.4% (31.5%; 49.2%) for N=24, 39.2% (29.6%; 48.9) for N=20, and 39.4% (28.8%; 50.0%) for N=16.

In addition, N=20 would also be sufficient to provide adequate precision for a between-panel difference in the relative change from baseline of at least 26% in case of large inter-subject variability.

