5.5. Exploratory Endpoints Analysis

5.5.1. Relationship Between Intrahepatic and Blood Markers

Relationships between intrahepatic and blood markers (Table 4) and/or their change from baseline at Week 40 will be evaluated graphically with scatter plots displaying individual associations.

Means on pooled individual data by study panel and overall mean will also be plotted on the same graph.

The following correlation coefficients will be calculated by study panel and overall for the different correlation scenarios:

- Pearson's correlation coefficient for two continuous variables.
- Phi correlation coefficient for two binary variables.
- Point biserial correlation coefficient for one binary variable and one continuous variable.

Potential relationship on the selected subgroups defined in Section 5.7.4 will also be explored using the same graphical approach.

The following markers will be considered, i.e., each intrahepatic marker will be plotted against each blood marker:

Table 4: List of Intrahepatic and Blood Markers of Interest

Intrahepatic Markers/Endpoints	Blood Markers/Endpoints
• Proportion of HBsAg+ hepatocytes at Week 40	• HBV DNA level at Week 40 (\log_{10})
• Change from Baseline at Week 40 in proportion of HBsAg+ hepatocytes	• HBV RNA level at Week 40 (\log_{10}) • HBsAg level at Week 40 (\log_{10})

 • Proportion of cccDNA-positive hepatocytes at Week 40 • Change from Baseline at Week 40 in proportion of cccDNA-positive hepatocytes • Proportion of pgRNA-positive hepatocytes at Week 40 • Change from Baseline at Week 40 in proportion of pgRNA-positive hepatocytes • pgRNA levels at Week 40 (\log_{10} copies/ cell) • Change from Baseline at Week 40 in pgRNA levels (\log_{10} copies/ cell) • 	
 • HBeAg level at Week 40 (\log_{10}) • HBcrAg level at Week 40 (\log_{10}) • Change from Baseline at Week 40 in HBV DNA (\log_{10}) • Change from Baseline at Week 40 in HBV RNA (\log_{10}) • Change from Baseline at Week 40 in HBsAg (\log_{10}) • Change from Baseline at Week 40 in HBeAg (\log_{10}) • Change from Baseline at Week 40 in HBcrAg (\log_{10}) • Maximum on-treatment ALT decrease • HBsAg seroclearance at FU Week 24
--	---

Additional markers and endpoints may be evaluated when data will be available.

5.5.2. Association Between Baseline Characteristics or Intrahepatic/Blood Markers with Efficacy Variables

The following list of efficacy endpoints of interest will be evaluated:

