Within each scenario, we set the percent of HBsAg+ hepatocytes at baseline and Week 40 for both Panels 1 and 2. From these four numbers (highlighted in **bold**), the remaining numbers in the table are derived. Data were simulated for each scenario using various sample sizes (assuming an equal number of subjects in each panel) and various values of SD_{slope} (standard deviation for the inter-subject random slope).

The true inter-subject variability of the intercept, $SD_{\text{intercept}}$, where $\xi_i \sim N(0, SD_{\text{intercept}})$, was set to 1.0 across all simulations based on the inter-subject differences observed from the donors data.

In contrast, inter-subject differences in the slopes are unknown, so a range of values of SD_{slope} were considered.

The number of HBsAg⁺ hepatocytes for subject i at visit j , denoted Y_{ij} , was simulated as $Y_{ij} \sim \text{Binomial}(N_{ij}, p_{ij})$, where N_{ij} is the total number of hepatocytes sampled during a biopsy. Based on the donors data, we simulated $\log(N_{i0}) \sim N(10, 0.35)$ for the baseline biopsy, and then $\log(N_{i1}) \sim N(\log(N_{i0}), 0.1)$ for the Week 40 biopsy; values of N_{i0} and N_{i1} were then rounded to integers.

Statistical Analysis of the Simulated Data

For each simulated dataset, we fit both the overall model as specified in Section 5.3.1.2.2.1 and the between-panel model as specified in Section 5.3.1.2.2.2. From the overall model, we estimated the absolute and relative reductions from baseline in the overall proportion of HBsAg⁺ hepatocytes. From the between-panel model, we estimated the between-panel differences in the reductions. For each estimate we obtained an 80% confidence interval (CI). Note that, for ease of interpretation, we present the changes from baseline as “reductions” – simply the negative of changes – so that most of the reported numbers are positive. I.e., a change from 75% to 5% is reported as an absolute reduction of 70% rather than as an absolute change of -70%.

We averaged all the estimates across 1000 simulations. The primary metric of interest is the width of the 80% CIs, which tell us how precisely we can estimate the reductions of interest given the sample size and the assumptions of the data-generating model.

Simulation Results

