ATTACHMENT 2. SELECTED MAJOR PROTOCOL DEVIATIONS FOR ANALYSIS PURPOSES

The major protocol deviations that may affect the assessment of efficacy will be finalized prior to the primary analysis database lock. The major deviations that are selected to exclude participants from the PP set are listed below.

Sequence No.	Protocol Deviation Description (DVTERM)	Protocol Deviation Coded Term (DVDECOD)	Exclude from PP
1	Inclusion criterion 3 not met: Participant had not confirmed chronic HBV infection. In addition, chronicity was not documented at least 6 months prior to screening.	Entered but did not satisfy criteria	Yes
2	Inclusion criterion 4 not met: For Panel 1 Participant not currently treated including treatment naïve participants was not: a. HBeAg positive, AND b. with serum HBV DNA at screening \geq 20,000 IU/mL, AND c. with ALT levels at screening $<$ 10x ULN, AND d. with indication for NA treatment according to local standard practice	Entered but did not satisfy criteria	Yes
3	Inclusion criterion 4.1 not met: For Panel 3 Participant not currently treated was not: a. HBeAg positive AND with serum HBV DNA at screening \geq 20,000 IU/mL OR HBeAg negative AND with serum HBV DNA at screening \geq 2,000 IU/mL, AND b. with ALT levels at screening $<$ 10x ULN, AND c. with indication for NA treatment according to local standard practice	Entered but did not satisfy criteria	Yes
4	Inclusion criterion 5 not met: For Panel 2 Virologically suppressed participant was not: a. HBeAg negative b. on stable HBV treatment, defined as currently receiving NA treatment (ETV, tenofovir disoproxil, or TAF) for at least 6 months prior to screening and have been on the same NA treatment regimen (at the same dose) for at least 3 months at the time of screening, AND c. with serum HBV DNA $<$ 60 IU/mL on 2 measurements at least 3 months apart (one of which is at screening), AND d. with documented ALT values $<$ 2.0x ULN on 2 measurements at least 3 months apart (one of which is at screening).	Entered but did not satisfy criteria	Yes

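### The overall liver–blood correlations in SAP 5.5.1 are not adjusted for panel, so for pairs where both markers differ by panel, mainly change-from-baseline pairs, they partly measure the panel gap

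*SAP*

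**What the plan says.** SAP 5.5.1 plans scatter plots and correlation coefficients for each intrahepatic marker against each blood marker in Table 4: "The following correlation coefficients will be calculated by study panel and overall for the different correlation scenarios". The list begins with "Pearson's correlation coefficient for two continuous variables"; phi and point-biserial coefficients cover binary markers. No adjustment for panel is given for the overall coefficient, and nothing says which coefficient answers the objective. Individual points, panel means and the overall mean go on the same graph.

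The panels differ by design. Of the first, the SAP Introduction says "Panel 1 will consist of participants who are HBeAg positive and not currently treated". The second takes HBeAg-negative people whose virus is already controlled on an NA. Screening HBV DNA is at least 20,000 IU/mL in Panel 1 and below 60 IU/mL in Panel 2 (Protocol 5.1; SAP Attachment 2).

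Other sections treat panel differently. Protocol 9.4.1.3 describes these correlations by study panel only, and SAP Appendix 2 reports no change from the protocol-planned analyses. SAP 5.5.2 puts panel in its logistic models. The repeated-measures model in SAP 5.4.2.4.1.1 includes HBV baseline status. HBeAg summaries in SAP 5.4.2.3, 5.4.2.4.1.1 and 5.4.2.4.3 are limited to participants HBeAg positive at entry; 5.5.1 does not repeat that limit.

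**The concern.** When two groups differ on both variables, pooling them produces a correlation even if the variables are unrelated inside each group. Enrolling two contrasting panels is enough to create it.

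How well blood markers track events in the liver is one of the questions that Protocol Section 2 gives as a reason for the study. After the 20% dropout assumed in SAP Attachment 1, each panel has 9 to 10 usable participants, so the by-panel coefficients will be imprecise. The overall figure has the largest n and, for the affected pairs, may be the largest value. A value near 0.5 could then be taken as support for a blood marker as a stand-in for a liver marker when it reflects only who was enrolled.

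HBeAg is an extra case. Panel 2 values below the LLOQ are imputed at 0.055 IU/mL (SAP Table 3). If they stay below it, their change is zero, and HBeAg acts largely as a panel label.

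**Working it through.** **1. Reproducing the plan's own figures.** The documents state no correlation. They do state precision figures from the model that supplies the liver-marker gap. The inputs are Scenario A, "Assuming an absolute reduction of 70% in Panel 1 (75% at baseline versus 5% at Week 40) and 29% in Panel 2" (30% to 1%); the slope SD, "assuming an inter-subject variability of the change equal to 0.5 on the logit scale in both panels"; and the intercept SD, which "was set to 1.0 across all simulations based on the inter-subject differences observed from the donors data". In 4,000 simulated trials per setting, with N=24:

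| Quantity | SAP Section 3 | Recomputed |
|---|---|---|
| Overall reduction (80% CI width) | 50.8% (16.7%) | 50.8% (16.6%) |
| Between-panel difference (80% CI width) | 40.4% (17.6%) | 40.2% (17.7%) |

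The model is therefore understood correctly.

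**2. Formula.** With equal panels and zero within-panel correlation, the pooled covariance is gap_x × gap_y / 4, and each pooled variance is the within-panel variance plus gap²/4. So

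pooled r = √(S_x × S_y), where S = (gap²/4) / (gap²/4 + within-panel variance),

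signed by the direction of the gaps.

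**3. Liver marker: change in HBsAg+ proportion.** Scenario A with slope SD 0.5 gives a mean change of −63.6 points (SD 13.8) in Panel 1 and −31.3 points (SD 17.2) in Panel 2. The gap is 32.3, so gap²/4 = 260.8. The mean within-panel variance is (13.8² + 17.2²)/2 = 243.1. S_x = 260.8/503.9 = 0.518, and √S_x = 0.719.

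**4. Blood marker: change in HBV DNA (log10).** This takes baseline at the screening limits and assumes that Panel 1 reaches about 15 IU/mL by Week 40.
- Panel 1 falls by at least log10(20,000/15) = 3.12.
- Panel 2 can fall by at most log10(60/5) = 1.08.
- The gap is then at least 3.12 − 1.08 = 2.04.

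The within-panel SD is not given, so 1.0 to 1.5 is assumed. The range includes 1.328, the SD of an HBsAg decline in another study quoted in Protocol Appendix 10.

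**5. Overall r with no within-panel association.** The formula was checked with 20,000 simulated trials per row at 12 per panel.

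| HBV DNA gap | SD | √S_y | Formula r | Simulated r |
|---|---|---|---|---|
| 2.0 | 1.5 | 0.555 | 0.40 | 0.41 |
| 2.5 | 1.328 | 0.685 | 0.49 | 0.50 |
| 2.0 | 1.0 | 0.707 | 0.51 | 0.52 |
| 2.5 | 1.0 | 0.781 | 0.56 | 0.57 |
| 3.0 | 1.0 | 0.832 | 0.60 | 0.61 |

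If an 80% Fisher interval were attached, it would exclude zero in 80% to 99% of trials, against a nominal 20% (74% to 98% at 10 per panel). A blood gap of 1 within-panel SD gives r = 0.33. No blood gap gives r = 0.00.

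**6. Panel-adjusted version.** On the same simulated data the partial correlation averages 0.00, and its 80% interval excludes zero in about 19% to 21% of trials.

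**7. Other SAP scenarios.** Let d be the liver-change gap in within-panel SDs over slope SDs 0.5 to 2.0, so S_x = (d²/4)/(d²/4 + 1). The lowest r uses √S_y = 0.555 and the highest uses 0.832.

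| Scenario | d | √S_x | Overall r |
|---|---|---|---|
| A | 1.4–2.1 | 0.57–0.72 | 0.32–0.60 |
| B | 1.9–3.7 | 0.69–0.88 | 0.38–0.73 |
| C | 0.6–1.3 | 0.29–0.55 | 0.16–0.45 |

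**8. Week 40 levels.** The liver gap is smaller here: 0.55 to 0.98 SD in A and 0.33 to 0.67 in C. In B it is −0.29 to −0.58, because the panel order reverses. At slope SD 0.5 with a blood gap of 1 to 3 SD, the induced r is about 0.20 to 0.37 in A and −0.12 to −0.23 in B. The documents give no Week 40 panel values for any blood marker.

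**The case against.** The best defence is that the safeguards are already in the same section. By-panel coefficients are planned, and the plots show individual points with panel means, so a between-panel artefact should be visible. The analysis is exploratory, no test is done (SAP 5.1.7), and 5.5.1 attaches no confidence interval to the correlations. All of this stands and limits the severity. It does not make the unadjusted number easier to interpret, and no rule ranks the coefficients.

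An overall figure is also legitimate. Protocol Section 3 and SAP 1.1.1 assess the objectives overall and by panel, and association across populations is a valid description. That stands too, so the overall coefficient should not be dropped.

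Several stronger readings are tempting but unsupported:
- A reader might infer that every overall correlation is spurious. The artefact needs both markers to differ by panel.
- A reader might size it from the assumed baseline levels: logit(0.75) − logit(0.30) = 1.95, against an SD of 1.0. Table 4 lists no baseline levels, and no scenario gives a Week 40 level gap that large.
- A reader might treat Panel 2 HBV DNA as a constant. Below the LLOQ of 20 IU/mL it takes 5 or 15 IU/mL, and entry allows values up to 60. Ties remain a weakness of any coefficient here, including a rank-based one.
- A reader might say the objective concerns a relationship within participants. The endpoint is association between levels and changes across participants; the relevant contrast is within panel versus pooled.

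**Conclusion.** The point holds for a defined set of pairs. Where both markers differ by panel, the unadjusted overall coefficient mixes the panel gap with any association inside the panels. For change in HBsAg+ proportion against change in HBV DNA, that alone gives about 0.4 to 0.6 at 12 per panel.

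The liver side of this figure comes from the SAP's Scenario A with slope SD 0.5. The blood side is assumed: a gap of 2 to 3 log10, which depends on Panel 1 reaching about 15 IU/mL, and a within-panel SD of 1.0 to 1.5. Under the same blood assumptions, the SAP's other scenarios and slope SDs widen the range to about 0.2 to 0.7. For Week 40 level pairs the documents do not support any general statement of size or sign.

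This is an inexpensive improvement to an exploratory analysis. It does not affect the primary endpoint.

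**What to change.** In SAP 5.5.1:
- State that the by-panel coefficients are the main result, consistent with Protocol 9.4.1.3.
- Keep the overall coefficient, label it as including between-panel differences, and report a panel-adjusted (partial) correlation beside it.
- Restrict pairs involving HBeAg to participants HBeAg positive at study entry, as in SAP 5.4.2. For Panels 1 and 2, the overall HBeAg coefficient then reduces to the Panel 1 coefficient.
- Apply the same labelling to the overall phi and point-biserial coefficients, which are pooled in the same way.

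The cost is a few sentences in the SAP, one extra column in the correlation tables and a small programming change. No additional data are needed.
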